3.2 Exclusion Criteria

Subjects are excluded from the study if any of the following criteria apply:

1. Has received prior therapy with an anti-PD-1, anti-PD-L1, or anti-PD-L2 agent or with an agent directed to another stimulatory or co-inhibitory T-cell receptor (e.g., CTLA-4, OX-40, CD137).
2. Prior therapy with a PI3K inhibitor

3. Has received prior chemotherapy, targeted small molecule therapy, or surgery within 4 weeks of the first dose of treatment. Participants must have recovered from all AEs due to previous interventions to \leq Grade 1 or baseline. Participants with \leq grade 2 neuropathy, anemia, and/or alopecia may be eligible.
4. Has received prior radiotherapy within 2 weeks of start of study treatment. Participants must have recovered from all radiation-related toxicities to \leq Grade 1 or baseline, not require corticosteroids, and not have had radiation pneumonitis. A 1-week washout is permitted for palliative radiation (\leq 2 weeks of radiotherapy) to non-CNS disease. Participants with \leq grade 2 neuropathy, anemia, and/or alopecia may be eligible.
5. Is currently participating in or has participated in a study of an investigational agent or investigational device within 4 weeks prior to the first dose of study treatment. (i.e. must be 4 weeks after the last dose of the previous investigational agent).
6. Has received a live vaccine within 30 days prior to the first dose of study drug. Seasonal influenza vaccines for injection are generally killed virus vaccines and are allowed; however, intranasal influenza vaccines (e.g., FluMist®) are live attenuated vaccines and are not allowed.
7. Has a known additional malignancy that is progressing or requires active treatment. Exceptions include basal cell carcinoma of the skin, squamous cell carcinoma of the skin, or carcinoma in situ (e.g. breast carcinoma, cervical cancer in situ) that have undergone potentially curative therapy.
8. Has known CNS metastases and/or carcinomatous meningitis.
9. Has symptomatic ascites or has required a paracentesis in the last 12 weeks
10. Has known hypersensitivity to nivolumab, copanlisib, or any ingredients in the formulation of these study drugs.
11. Has a diagnosis of immunodeficiency or is receiving chronic systemic steroid therapy (in dosing exceeding 10 mg daily of prednisone equivalent) or any other form of immunosuppressive therapy within 7 days prior to the first dose of study drug.

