4.4.4 Additional Toxicity Monitoring and Prevention

4.4.4.1 Glucose and Diet Monitoring

Period	Fasting \geq 12 h required before first glucose measurement	Pre-dose glucose levels
Day 1 of Cycle 1	Yes	<125 mg/dL (non-diabetic patients) <160 mg/dL (diabetic patients)
Subsequent infusions after Cycle 1 Day 1	Yes	<160 mg/dL (fasting) <200 mg/dL (non-fasting)

Fasting refers to a \geq 12 hour fast. Non-fasting status includes any caloric intake such as meals, juice, snack, as well as other caloric intake not consistently called a meal.

From Cycle 1 Day 1 onwards, glucose measurements may be done either by laboratory analysis or in capillary blood.

Because of its inhibitory effect on the PI3K α -isoform, which is implicated in insulin metabolism, copanlisib infusions could be associated with a temporary increase in blood glucose. Addition of a meal in close proximity to copanlisib infusion may exacerbate glucose increase.

On infusion days a low calorie or low carbohydrate diet is recommended. It is recommended that timing and content of caloric intake as well as additional glucose testing (if clinically indicated) on infusion days is monitored by the investigators based on glucose response patterns during prior treatment days. Consultation with a diabetologist or endocrinologist is advised.

All glucose measurements, oral glucose lowering medication and/or insulin administration, if applicable, fasting/non-fasting status, and meal intake timing on infusion days will be collected as part of the clinical source documentation.

Glucose monitoring on study

Management of hyperglycemia and dose delay parameters are outlined in **Table 4**

The following assessments should be performed on Day 1, 8, and 15 of each cycle before receiving copanlisib unless otherwise specified:

- Patients should be fasting for at least 12 hours prior to the pre-dose glucose measurement. For details on fasting requirements and glucose measurement during C1D1 please refer to **Table 6**
- Blood glucose will be measured at 0 hours (pre-dose) and 1 hour after completion of copanlisib (+/- 15min) infusion. If 1 hour post-infusion blood glucose is \geq 35 mg/dL higher than pre-dose level, recheck in another hour (2 hours post-infusion) to ensure decline in blood glucose. Additional measurements to be performed as clinically indicated.

NOTE: If patient needs to take a low glycemic meal, then glucose test should be taken prior to meal intake.

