5.1 Definitions

5.1.1 Adverse Event

An adverse event (AE) is defined as any undesirable sign, symptom or medical condition occurring after starting the study drug (or therapy) even if the event is not considered to be related to the study. An undesirable medical condition can be symptoms (e.g., nausea, chest pain), signs (e.g., tachycardia, enlarged liver) or the abnormal results of an investigation (e.g., laboratory findings, electrocardiogram). Medical conditions/diseases present before starting the study treatment are only considered adverse events if they worsen after starting the study treatment (any procedures specified in the protocol). Symptoms / medical conditions occurring before starting the study treatment but after signing the informed consent form will not be recorded as AEs. Additionally, expected progression of the disease being studied will not be recorded as an adverse event.

Laboratory abnormalities: Laboratory abnormalities present at the screening visit will be recorded as pre-treatment signs and symptoms in a medical history CRF. After study treatment administration, all grade 3 and 4 clinical laboratory results that represent an increase in severity from baseline will be reported as adverse events. A grade 1 or 2 clinical laboratory abnormality should be reported as an adverse event only if it is considered clinically significant by the investigator, induces clinical signs or symptoms, or requires therapy.

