11.3 Safety Analyses

AE data will be listed individually and incidence of AEs will be summarized by system organ class and preferred terms within a system organ class for Phase I and Phase II (overall and within each cohort). When calculating the incidence of AEs, each AE will be counted only once for a given subject. In analyses of grade and causality, if the same AE occurs on multiple occasions, the highest grade and strongest relationship to study drug will be assumed. If 2 or more AEs are reported as a unit, the individual terms will be reported as separate experiences. Incidence, measured as time to first AE, will be analyzed for all AEs and by type using the methods described above. In addition, the event rates (which incorporate multiple AEs of the same type) will be analyzed using Negative Binomial regression.

Changes in vital signs, hematology and clinical chemistry parameters from baseline to the end of the study will be examined. Toxicity will be tabulated by type and grade. Toxicities will be characterized according to the CTCAE version 5.0. Treatment-emergent changes from normal to abnormal values in key laboratory parameters will be identified. Incidence and rate evaluations will follow the methods described for AEs.

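### Section 11.3's laboratory shift summary names only normal-to-abnormal changes, so low-grade worsening from an abnormal baseline can go uncounted, and the use of post-infusion values is left open

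*Combined protocol and SAP*

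**What the plan says.** Section 11.3 (Safety Analyses) gives three summaries that bear on laboratory values and vital signs:

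- Change over time: "Changes in vital signs, hematology and clinical chemistry parameters from baseline to the end of the study will be examined".
- Graded toxicity: "Toxicity will be tabulated by type and grade", and "Toxicities will be characterized according to the CTCAE version 5.0".
- Laboratory shifts: "Treatment-emergent changes from normal to abnormal values in key laboratory parameters will be identified".

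The paragraph closes by applying the adverse event (AE) incidence and rate methods. For AEs, the same section states that "if the same AE occurs on multiple occasions, the highest grade and strongest relationship to study drug will be assumed".

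Section 5.1.1 decides which laboratory results become AEs. After treatment starts, "all grade 3 and 4 clinical laboratory results that represent an increase in severity from baseline will be reported as adverse events". A Grade 1-2 abnormality becomes an AE only if the investigator judges it clinically significant, it causes signs or symptoms, or it needs therapy. Section 5.3 has every change of grade within an AE recorded.

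The laboratory table in Section 3.1 allows AST/ALT up to 3 x ULN, total bilirubin up to 1.5 x ULN, platelets from 75 000/µL, hemoglobin from 8.0 g/dL and fasting glucose below 160 mg/dL. Section 3.2 (items 3 and 4) says that patients with anemia up to Grade 2 may be eligible.

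Section 4.4.4.1 notes that "copanlisib infusions could be associated with a temporary increase in blood glucose". It measures glucose before each copanlisib infusion and 1 hour after, with a 2-hour recheck if the rise is 35 mg/dL or more. Section 4.4.4.2 measures blood pressure before, during and at the end of each infusion, and 1 and 2 hours later.

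**The concern.** A patient who is abnormal at baseline cannot move from normal to abnormal, however far the value worsens. Phase II patients have had at least two prior lines of therapy, and the entry limits expressly admit such baselines. The one shift rule the plan names therefore says nothing about these patients.

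The change-from-baseline sentence raises a second question. Hyperglycemia and hypertension are among the most common drug-related events that Section 2.1 lists for single-agent copanlisib, each in more than 20% of patients, and the protocol samples for them within hours of infusion. If the comparison uses only the last value, those samples play no part in it.

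At stake is the secondary objective of characterizing the combination's toxicities (Section 1.2), and the like-for-like reading of laboratory findings in Cohorts A and B.

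**Working it through.** The plan gives no figure to reproduce. The check is to trace each kind of laboratory change through Sections 5.1.1 and 11.3.

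| Change on treatment | Shift summary (11.3) | AE tables (5.1.1, 11.3) |
|---|---|---|
| (a) Normal baseline to abnormal, including a transient peak | Can be counted; no time limit is stated | If it qualifies as an AE |
| (b) Abnormal baseline, worsens to Grade 3-4 | Not counted | Counted, at highest grade |
| (c) Abnormal baseline, worsens within Grade 1-2; significant, symptomatic or treated | Not counted | Counted |
| (d) Abnormal baseline, worsens within Grade 1-2; none of these | Not counted | Not counted |
| (e) Glucose rise after infusion from an abnormal baseline; asymptomatic, untreated | Not counted | Not automatically: Table 4 words this as Grade 1 |

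Rows (d) and (e) are the gap. For glucose the opening is narrower than the entry limit suggests, because Section 4.4.1 delays the first dose in non-diabetic patients whose fasting glucose exceeds 125 mg/dL.

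**Timing.** Section 11.3 does not say whether its change summary uses the last value, every visit or the worst value. Under a last-value reading, the final measurement would be at the End of Treatment visit, about 30 days after the last infusion (Section 4.6). In both calendars (Sections 8.1 and 8.2), the timed glucose row and the infusion-day blood pressure row have no entry at baseline or End of Treatment. Such a comparison could use only the chemistry-panel glucose and the routine vital signs. Under an all-visits reading, the post-infusion values could be included. Blood pressure is not a laboratory value, so neither the shift sentence nor the laboratory rules of 5.1.1 apply to it. It depends on the general AE definition and on this sentence.

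**Why no size can be given.** Let a be the fraction abnormal at baseline and w the fraction that worsens, taken as independent of baseline and, for patients normal at baseline, as equivalent to becoming abnormal. Neither is in the documents; the values below are assumptions.

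- All treated patients in the denominator: shift rate = w(1 - a). With w = 40% and a = 30%, 50%, 70%, this is 0.40 x 0.70 = 28%, 0.40 x 0.50 = 20% and 0.40 x 0.30 = 12%.
- Only baseline-normal patients in the denominator: w(1 - a)/(1 - a) = w = 40% for every a.
- Two cohorts with w = 40% and a = 30% and 60%: 28% against 0.40 x 0.40 = 16% under the first denominator, and 40% against 40% under the second.

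Section 11.3 does not state the denominator, so even the existence of a numerical understatement in the shift rate is undetermined. These figures concern the shift summary alone, not the AE tables.

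**The case against.** The strongest reply is that the shift sentence is one supplementary summary among several, and that the plan's main route for laboratory toxicity does not require a normal baseline. That is right, and it rules out three stronger readings.

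First, a reader might infer that worsening from an abnormal baseline is never counted. Section 5.1.1 uses increase in severity from baseline for Grade 3-4 results, and Section 11.3 tabulates toxicity by grade and takes the highest grade when an AE recurs. A patient entering with ALT at 1.5 x ULN and reaching 10 x ULN would be missing from the shift summary but would very likely be in the AE tables. That value is well above the 3 x ULN dose-delay limit in Section 4.4.1, and an event that stops dosing is hard to call clinically insignificant.

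Second, a reader might infer that transient post-infusion peaks are missed. That follows only under a last-value reading of an ambiguous sentence. The shift sentence has no time limit, treated glucose peaks are AEs because they needed therapy, and a blood pressure rise can be reported as an undesirable sign.

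Third, a reader might infer that laboratory toxicity is understated by the baseline-abnormal fraction, or that the cohorts would differ for that reason alone. With a baseline-normal denominator both effects vanish.

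The reply does not reach rows (d) and (e). There, capture rests on the investigator's judgment of significance rather than on the measured value. Such changes need not be trivial: Table 4 withholds treatment for Grade 2 neutropenia or thrombocytopenia on Day 1 of a cycle, while 5.1.1 does not make a Grade 2 result an AE automatically.

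**Conclusion.** The concern holds in a narrow form. The named shift rule cannot register worsening in patients whom the entry criteria admit with abnormal values. Low-grade worsening that is not judged significant and is neither symptomatic nor treated, and the corresponding glucose rises after infusion, can appear in neither the shift summary nor the AE counts. Whether post-infusion glucose and blood pressure enter the change-from-baseline summary is not stated.

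This is a minor reporting gap in a descriptive analysis, and its size cannot be established from the documents. It leaves the DLT definition (Section 4.3), the Bayesian stopping guideline (Section 11.4), and the sample size and efficacy rules untouched. The conclusion rests on taking the shift sentence as worded and on the AE filter in Section 5.1.1 being applied as written.

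**What to change.** In Section 11.3, replace the normal-to-abnormal sentence with:

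*Treatment-emergent laboratory toxicity is any increase in CTCAE v5.0 grade over baseline at any time from first dose to the EOT visit; shift tables of baseline grade by worst post-baseline grade will be given for each parameter.*

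State the denominator alongside it. Amend the change-from-baseline sentence to say that all scheduled values are used. Add a summary of the maximum post-infusion glucose and blood pressure, and of their change from the same-day pre-dose value. The glucose summary is needed as well as the grade shift because Table 4 words Grade 1 hyperglycemia by symptoms and intervention, not by level, so grade alone does not show how large an untreated rise was.

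The cost is a few lines of text and a few extra standard tables. The values are already scheduled for collection, and no visit, sample or decision rule changes.

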11.4 Safety Monitoring

The proportion of treated subjects with unacceptable toxicity will be monitored using a Bayesian stopping guideline within each cohort (Cohort A: colorectal cancer with PIK3CA mutation and Cohort B: WT PIK3CA with known lack of sensitivity to immune checkpoint inhibitor therapy) separately during Phase II. A $\beta(1.5, 5.5)$, representing a toxicity rate of 21%, the slightly higher than the expected toxicity rate, was used in the development of our guidelines. These guidelines will recommend that recruitment be halted and the trial be

reassessed if the posterior probability that the unacceptable toxicity rate exceeds the maximum allowable rate (33%) is greater than 0.55. Once the initial 6 patients are recruited, toxicity will be monitored continuously. **Table 11** summarizes the stopping boundaries for unacceptable toxicities.

Table 11: The number of toxicities needed to trigger stopping guidelines throughout the course of the study within each cohort.

Number of Subjects Per Cohort	Number of toxicities needed to trigger re-evaluation
6-8	4
9-11	5
12-14	6
15-17	7
18-20	8
21	9

The probability of triggering the stopping guidelines was assessed for a range of possible true toxicity rates using simulations with 10,000 replicates (**Table 12**). The probability of stopping to re-evaluate was 9.5% if the true proportion with an unacceptable toxicity was 20%, the expected level. In comparison, the probability of stopping early is 54% and 70% if the true proportion with an unacceptable toxicity was 35% or 40%, i.e. above the 33% threshold.

Table 12: Probability of triggering a re-evaluation based upon the proportion with an unacceptable toxicity for a range of true toxicity probabilities.

True probability of unacceptable toxicity	Probability of triggering stopping guidelines
5%	< 0.1%
10%	0.8%
15%	3.1%
20%	9.5%
25%	21%
30%	37%
35%	54%
40%	70%

APPENDIX A: Performance Status Criteria

ECOG Performance Status Scale		Karnofsky Performance Scale	
Grade	Descriptions	Percent	Description
0	Normal activity. Fully active, able to carry on all pre-disease performance without restriction.	100	Normal, no complaints, no evidence of disease.
		90	Able to carry on normal activity; minor signs or symptoms of disease.
1	Symptoms, but ambulatory. Restricted in physically strenuous activity, but ambulatory and able to carry out work of a light or sedentary nature (e.g., light housework, office work).	80	Normal activity with effort; some signs or symptoms of disease.
		70	Cares for self, unable to carry on normal activity or to do active work.
2	In bed <50% of the time. Ambulatory and capable of all self-care, but unable to carry out any work activities. Up and about more than 50% of waking hours.	60	Requires occasional assistance, but is able to care for most of his/her needs.
		50	Requires considerable assistance and frequent medical care.
3	In bed >50% of the time. Capable of only limited self-care, confined to bed or chair more than 50% of waking hours.	40	Disabled, requires special care and assistance.
		30	Severely disabled, hospitalization indicated. Death not imminent.
4	100% bedridden. Completely disabled. Cannot carry on any self-care. Totally confined to bed or chair.	20	Very sick, hospitalization indicated. Death not imminent.
		10	Moribund, fatal processes progressing rapidly.
5	Dead.	0	Dead.

APPENDIX B: Contraceptive Guidance and Pregnancy Testing

Woman of Childbearing Potential (WOCBP)

A woman is considered fertile following menarche and until becoming post-menopausal unless permanently sterile (see below)

Women in the following categories are not considered WOCBP:

- Premenarchal
- Premenopausal female with 1 of the following:
 - Documented hysterectomy
 - Documented bilateral salpingectomy
 - Documented bilateral oophorectomy

Note: Documentation can come from the site personnel's review of the participant's medical records, medical examination, or medical history interview.

- Postmenopausal female
 - Defined as no menses for 12 months without an alternative medical cause.
 - Females on HRT and whose menopausal status is in doubt will be required to use one of the non-hormonal highly effective contraception methods if they wish to continue their HRT during the study. Otherwise, they must discontinue HRT to allow confirmation of postmenopausal status before study enrollment.

Contraception Requirements

Male Participants:

Male participants with female partners of childbearing potential are eligible to participate if they agree to one of the following for the duration of the study and for 7 months after last dose of study drug:

- Agree to be abstinent from penile-vaginal intercourse as their usual and preferred lifestyle (abstinent on a long term and persistent basis) and agree to remain abstinent
- Agree to use a male condom plus partner use of a contraceptive method with a failure rate of <1% per year as described in Table 8 when having penile-vaginal intercourse with a woman of childbearing potential who is not currently pregnant.
 - Note: Men with a pregnant or breastfeeding partner must agree to remain abstinent from penile-vaginal intercourse or use a male condom during each episode of penile penetration.

Note: male participants will be considered to be of non-reproductive potential if they have azoospermia (whether due to having had a vasectomy or due to an underlying medical condition).

Female Participants:

Female participants of childbearing potential are eligible to participate if they agree to use a highly effective method of contraception consistently and correctly as described in **Table 13** for the duration of the study and for 5 months after last dose of study drug:

Table 13 - Highly Effective Contraception Methods


Highly Effective Contraceptive Methods That Are User Dependent ^a Failure rate of < 1% per year when used consistently and correctly.
 
 ● Combined (estrogen- and progestogen- containing) hormonal contraception ^{b, c} 
 ○ Oral ○ Intravaginal ○ Transdermal ○ Injectable ● Progestogen-only hormonal contraception ^{b, c} 
 ○ Oral ○ Injectable

Highly Effective Methods That Have Low User Dependency Failure rate of <1% per year when used consistently and correctly.
 
 ● Progestogen- only contraceptive implant ^{b, c} ● Intrauterine hormone-releasing system (IUS) ^b ● Intrauterine device (IUD) ● Bilateral tubal occlusion

 ● Vasectomized partner A vasectomized partner is a highly effective contraception method provided that the partner is the sole male sexual partner of the WOCBP and the absence of sperm has been confirmed. If not, an additional highly effective method of contraception should be used.

 ● Sexual abstinence Sexual abstinence is considered a highly effective method only if defined as refraining from heterosexual intercourse during the entire period of risk associated with the study treatment. The reliability of sexual abstinence needs to be evaluated in relation to the duration of the study and the preferred and usual lifestyle of the participant.)

Notes: Use should be consistent with local regulations regarding the use of contraceptive methods for participants of clinical studies.
 
a) Typical use failure rates are lower than perfect-use failure rates (i.e. when used consistently and correctly).
 
b) If hormonal contraception efficacy is potentially decreased due to interaction with study treatment, condoms must be used in addition to the hormonal contraception during the treatment period and for at least 120 days after the last dose of study treatment.
 
c) If locally required, in accordance with Clinical Trial Facilitation Group (CTFG) guidelines, acceptable hormonal contraceptives are limited to those which inhibit ovulation.

Pregnancy Testing

WOCBP should only be included after a negative highly sensitive urine or serum pregnancy test. Following initiation of treatment, pregnancy testing will be performed whenever an expected menstrual cycle is missed or when pregnancy is otherwise suspected, after the last dose of study treatment, and as required locally.

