1.5 Study Design

This is a multi-center, open-label, Phase I/II study. Phase 1 consists of a 3+3 dose de-escalation design to determine the dose of copanlisib for use in combination with nivolumab. Approximately 6-18 subjects with solid tumors will be treated in Phase I and will be monitored for dose limiting toxicities (DLTs) through their first cycle of treatment. Complete information on the definition of DLTs and dose de-escalation rules can be found in **Section 4.3**.

The Phase II portion of the study will evaluate the safety and clinical activity of copanlisib and nivolumab in two cohorts of patients with previously treated metastatic colon cancer. Cohort A will enroll patients with PI3K mutation and Cohort B will enroll patients with wildtype PI3K status. Twenty-one patients are targeted for enrollment in each cohort, for an approximate total of 42 patients in Phase II. Enrollment in Phase II will be initiated once the recommended phase II dose (RP2D) has been determined in Phase I.

For all patients, the study will consist of a screening period, a treatment period, and a follow-up period. Screening evaluations will be done within 28 days prior to the start of study treatment.

Each treatment cycle is 28 days. Patients in both Phase I and Phase II will receive nivolumab on Day 1 of each cycle (every 4 weeks) and copanlisib on either Day 1, Day 8, and Day 15 of each cycle (3 week on, one week off) or on Day 1 and 15 of each cycle (every 2 weeks), depending on the dose level and RP2D. Complete information on study drug administration, schedule, and dosing can be found in **Section 4.2**.

Phase II enrollment will be carried out in 2 stages so that the study can terminate early if the combination of copanlisib and nivolumab is not sufficiently effective. In the first stage, 12 subjects will be accrued to each cohort. If there are no responders among the first 12 patients, the study will be terminated for futility. Otherwise, 9 additional patients will be accrued for a total of 21 treated subjects. If ≥ 3 out of the 21 patients have a response, then the trial will be considered a success for that cohort.

Clinical and immune responses will be evaluated at baseline and during treatment through tumor assessments, biopsies, and PBMC and plasma collection. Tumor assessments will be made using RECIST 1.1.

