International normalized ratio (INR) and partial thromboplastin time (PTT)	$\leq 1.5 \times \text{ULN}$ unless participant is receiving anticoagulant therapy as long as PT or aPTT is within therapeutic range of intended use of anticoagulants
Cardiac	
Left ventricular ejection fraction (LVEF)	$\geq 50\%$
^a Criteria must be met without erythropoietin dependency and without packed red blood cell (pRBC) transfusion within last 1 week.	
^b Creatinine clearance (CrCl) should be calculated per institutional standard.	

10. Male subjects must agree to use a contraception as detailed in **Appendix B** of this protocol during the treatment period and for at least 6 months after the last dose of study drug and refrain from donating sperm during this period.
11. Female subjects must not be pregnant (negative urine or serum test within 72 hours of first dose of study drug) or breastfeeding, and at least one of the following conditions must apply:
 - a. Not a woman of childbearing potential (WOCBP) as defined in **Appendix B or**
 - b. A WOCBP who agrees to follow the contraceptive guidance in **Appendix B** during the treatment period and for at least 6 months after the last dose of study drug.

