25. Patients with evidence or history of bleeding diathesis. Any hemorrhage or bleeding event \geq CTCAE Grade 3 within 4 weeks prior to the start of study medication
26. Had a blood or platelet transfusion within 7 days of Cycle 1 Day 1 treatment
27. Seizure disorder requiring anti-seizure medication
28. Has known psychiatric or substance abuse disorders that would interfere with cooperation with the requirements of the trial.

29. Has a history or current evidence of any condition, therapy, or laboratory abnormality that might confound the results of the study, interfere with the subject's participation for the full duration of the study, or is not in the best interest of the subject to participate, in the opinion of the treating investigator.
30. Is pregnant or breastfeeding, or expecting to conceive or father children within the projected duration of the study, starting with the screening visit through 6 months after the last dose of trial treatment
31. Is a prisoner or is compulsorily detained

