4.7 Duration of Follow Up

Subjects who discontinue from treatment should continue to follow up with their primary oncologist and be contacted every 3 months (+/- 2 weeks) to monitor OS for up to 3 years or death, whichever occurs soonest. Effort should be made to collect information regarding disease status until the start of new anti-neoplastic therapy, disease progression, death, or end of study. Information regarding post-study anti-neoplastic treatment will be collected if new treatment is initiated.

Subjects who are discontinued from the study treatment due to an unacceptable drug-related AE will be monitored for safety until the resolution of the AE to \leq grade 1, or stabilization, or until initiation of a new therapy for their cancer, whichever occurs first.

All subjects will be followed for at least 30 days after their last dose of study drug for the development of AEs. SAEs that occur within 100 days (+ 14 day reporting window) of the last infusion of nivolumab or before initiation of a new antineoplastic treatment should also be followed and recorded.

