5.6.2 Pregnancy Reporting

Although pregnancy and lactation are not considered adverse events, it is the responsibility of investigators or their designees to report any pregnancy or lactation in a subject (spontaneously reported to them), including the pregnancy of a male subject's female partner who has provided written consent to provide information regarding pregnancy, that occurs during the trial or within 6 months of completing the trial. All subjects who become pregnant must be followed to the completion/termination of the pregnancy. Pregnancy outcomes of spontaneous abortion, missed abortion, benign hydatidiform mole, blighted ovum, fetal death, intrauterine death, miscarriage and stillbirth must be reported as serious adverse events (Important Medical Events). Pregnancy and non-serious pregnancy outcomes should be reported as Events of Clinical Interest. If the pregnancy continues to term, the outcome (health

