20. Blood for PBMC and plasma will be collected at baseline/prior to first dose, 2 weeks after first dose, on Day 1 of each odd cycle, and at progression or EOT visit.
21. EOT Clinical assessments do not need to be repeated if they were done within last 7 days. Hemoglobin A1C, 12-lead ECG, and MUGA or echocardiogram do not need to be repeated if they were done within the last 4 weeks.
22. Subjects who discontinue treatment will be followed (by phone, email or visit) every 12 weeks (\pm 2 weeks) after completion of EOT visit for up to 2 years or study closure to monitor overall survival. Information on other cancer therapies and disease status will also be collected. In addition, SAEs that occur within 100 days (+14 day reporting window) of the end of treatment or before initiation of a new antineoplastic treatment should also be followed and recorded.

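### Appendix B asks women of childbearing potential for 5 months of contraception after the last dose; eligibility item 11b, which cites Appendix B, requires at least 6

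*Combined protocol and SAP*

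**What the plan says.** Four places in the combined protocol and SAP bear on how long women must avoid pregnancy after treatment.

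- **Appendix B, Female Participants.** A woman of childbearing potential is eligible if she agrees to use a highly effective method "for the duration of the study and for 5 months after last dose of study drug".
- **Section 3.1, item 11b.** A woman of childbearing potential must agree to follow the Appendix B guidance "during the treatment period and for at least 6 months after the last dose of study drug".
- **Section 3.2, item 30.** Anyone pregnant, breastfeeding or expecting to conceive is excluded over a window "starting with the screening visit through 6 months after the last dose of trial treatment".
- **Section 5.6.2.** The investigator must report any pregnancy "that occurs during the trial or within 6 months of completing the trial".

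Appendix B does not define the duration of the study. Section 1.5 says that for all patients "the study will consist of a screening period, a treatment period, and a follow-up period". Section 4.7 follows patients "to monitor OS for up to 3 years or death, whichever occurs soonest", while note 22 to the Phase II calendar (Section 8.2) follows them "for up to 2 years or study closure to monitor overall survival".

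**The concern.** Item 11b and the female paragraph of Appendix B are both written as conditions of eligibility, and the first relies on the second. On the plain reading, a woman who agrees to exactly 5 months after her last dose qualifies under Appendix B and fails item 11b. No text ranks one above the other.

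What is at stake is a participant-safety instruction. Appendix B holds the detailed guidance on methods, so it is a likely source for counselling, and the stop date matters long after the eligibility checklist has been filed. A woman counselled from Appendix B alone could stop contraception about a month before the protocol's own minimum. No statistical quantity depends on this.

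**Working it through.** The protocol gives no calculated figure to reproduce. The check is a comparison of texts plus simple date arithmetic.

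**Step 1: compare the post-dose periods.**

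| Place | Applies to | Period after treatment |
|---|---|---|
| Section 3.1, item 11b | Women of childbearing potential | At least 6 months after last dose |
| Section 3.2, item 30 | All participants | 6 months after last dose |
| Appendix B, female paragraph | Women of childbearing potential | 5 months after last dose |
| Section 3.1, item 10 | Men | At least 6 months after last dose |
| Appendix B, male paragraph | Men | 7 months after last dose |

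For men, 7 months satisfies a minimum of 6, so the two texts can both be obeyed. For women, 5 months does not satisfy a minimum of 6. The female figure in Appendix B is the only one below the criterion that cites it. Note b under Table 13 (condoms in addition to hormonal contraception for at least 120 days) is a separate, added precaution and does not resolve the difference.

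Section 5.6.2 also uses 6 months, but it counts from completion of the trial and is a reporting duty. It is weak support and is not relied on here.

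**Step 2: size the gap when the duration of the study means the treatment period.** One month is taken as 30.44 days.

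- Appendix B: 5 × 30.44 = 152.2 days
- Item 11b: 6 × 30.44 = 182.6 days
- Shortfall: 182.6 − 152.2 = 30.4 days

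**Step 3: size the gap when it includes follow-up.** Contraception would then continue throughout survival follow-up, so a woman still being followed at 6 months has a shortfall of 0. The requirement could overshoot instead: 24 − 6 = 18 months beyond item 11b's minimum under note 22 of Section 8.2, or 36 − 6 = 30 months under Section 4.7. For a woman who leaves follow-up before 6 months, the shortfall lies between 0 and 30.4 days.

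**Step 4: set the gap against drug exposure.** Section 2.2 gives nivolumab's geometric mean elimination half-life as 25 days, with a CV of 77.5%.

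- At the mean: 152.2 / 25 = 6.1 half-lives by 5 months; 182.6 / 25 = 7.3 by 6 months.
- One standard deviation above the mean on the log scale, assuming a log-normal distribution: σ = √ln(1 + 0.775²) = 0.686, so the half-life is 25 × e^0.686 = 49.6 days. Then 152.2 / 49.6 = 3.1 half-lives and 182.6 / 49.6 = 3.7.

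Neither result demonstrates harm from the missing month. Copanlisib's half-life is not in the visible text, so the same check cannot be made for it.

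**Step 5: table reference (clerical).** The male paragraph of Appendix B requires a partner method with "a failure rate of <1% per year as described in Table 8". Table 8, in Section 7.5.1, lists activating PIK3 mutations. The contraceptive methods are in Table 13.

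**The case against.** The strongest reply is that the operative rule is already 6 months. Section 3.1 requires every criterion to be met. Item 11b states its own period and can be read as taking the methods from Appendix B and the duration from itself. Exclusion item 30 applies 6 months again. A woman who agreed only to 5 months would not be enrolled, so Appendix B cannot lower the entry requirement.

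That is correct about entry, and it limits the weight of the point. It does not make the two texts agree, and it does not govern what a woman is told when treatment ends. The consent pages are not part of the copy reviewed, so actual counselling is unknown. Their absence counts neither for nor against the plan.

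A second reply is that the study includes follow-up, so Appendix B may in fact require longer contraception than item 11b. This reading is possible and is why the range starts at zero. It is the less natural one, because it makes the 5-month clause redundant for anyone who remains in follow-up and implies contraception for two or three years, which nothing else in the protocol supports.

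A third reply is that no harm is shown. That stands.

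**Conclusion.** The inconsistency is real and should be corrected. Appendix B's post-dose period for women is one month below the minimum in the criterion that cites it, and the protocol does not say which prevails.

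The shortfall is about 30 days if the duration of the study means the treatment period, and nil for a woman still in follow-up at 6 months if it includes follow-up. A practical consequence depends on three assumptions that the documents cannot settle: the treatment-period reading, counselling from Appendix B alone, and no later reminder of the 6-month commitment made at entry.

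**What to change.** In the female paragraph of Appendix B, replace the present period with item 11b's wording: "during the treatment period and for at least 6 months after the last dose of study drug". This corrects the number and removes the undefined reference to the duration of the study. Confirm that the consent form states the same period.

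In the same edit, change the male paragraph's reference from Table 8 to Table 13. The sponsor may also wish to replace the same undefined phrase there and decide whether men are to follow 6 or 7 months, although those two figures do not conflict.

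The cost is one sentence and one table number in Appendix B, plus the consent-form check.
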